
**LIST OF ABBREVIATIONS AND DEFINITION OF TERMS**

AE	Adverse Event
AESI	Adverse Event of Special Interest
ALT	Alanine amino Transferase
ANOVA	ANalysis Of VAriance
AST	Aspartate amino Transferase
ATC	Anatomical Therapeutic Chemical
BUN	Blood Urea Nitrogen
BMI	Body Mass Index
BW	Body Weight
CA	Competent Authority
CI	Confidence Interval
eCRF	(electronical) Case Report Form
CRO	Contract Research Organization
CSR	Clinical Study Report
E%	Percentage enhancement of lesion
eGFR	estimated Glomerular Filtration Rate
EMA	European Medicine Agency
FAS	Full Analysis Set
FDA	Food and Drug Administration
GBCA	Gadolinium Based Contrast Agent
HLGT	High-Level Group Term
HLT	High-Level Term
IBR	Independent Blinded Reader
ICH	International Conference on Harmonization
IMP	Investigational Medicinal Product
IWRS	Interactive Web Response System
LBK	Lesion to Background Ratio
LDH	Lactate Dehydrogenase
LLT	Lower Level Term
MCV	Mean red blood Cells Volume
MedDRA	Medical Dictionary for Regulatory Activities
MRI	Magnetic Resonance Imaging
PPS	Per Protocol Set
PT	Preferred Term
RBCs	Red Blood Cells
SAE	Serious Adverse Event
SAP	Statistical Analysis Plan
SS	Safety Set
SD	Standard Deviation
SOC	System Organ Class
SPS	Screened Patient Set
TEAE	Treatment Emergent Adverse Event
WBCs	White Blood Cells
WHO-DD	World Harmonization Organization Dictionary Drug

## 1. SUMMARY OF THE TRIAL PROTOCOL

This document presents the statistical analysis plan (SAP) for Guerbet, Protocol No. GDX-44-011 “Efficacy and Safety of Gadopiclenol for Body Magnetic Resonance Imaging (MRI) Phase III Clinical Trial”.

This analysis plan is based on the Protocol Version N° 3.0 dated June 30, 2020 and the amendment for FRANCE dated June 30, 2020.

### 1.1. Trial objectives

As this is a multi-regional trial and in order to meet with the respective requirements of regulatory authorities within one single protocol, trial objectives are presented in sub-section.

#### 1.1.1. Primary objectives

##### Primary objective 1:

- To demonstrate the superiority of gadopiclenol-enhanced MRI at 0.05 mmol/kg body weight (BW) compared to unenhanced MRI for patients referred for MRI of body regions, in terms of 3 lesion visualization co-primary criteria (border delineation, internal morphology and degree of contrast enhancement) using the patient as his/her own control.

##### Primary objective 2:

- To demonstrate the non-inferiority of gadopiclenol at 0.05 mmol/kg BW compared to gadobutrol at 0.1 mmol/kg BW in terms of 3 lesion visualization co-primary criteria (border delineation, internal morphology, degree of contrast enhancement) for patients referred for MRI of body regions.

For Food and Drug Administration (FDA), the primary objective 1 is to be achieved. The primary objective 2 will serve as one of the secondary objectives.

For European Medicine Agency (EMA), both primary objectives 1 and 2 are to be achieved.

#### 1.1.2. Secondary Objectives

- To demonstrate the non-inferiority of gadopiclenol compared to gadobutrol in terms of 3 lesion visualization co-primary criteria (border delineation, internal morphology, degree of contrast enhancement) for patients referred for MRI of the body regions (idem primary objective 2, considered as secondary objective for FDA).
- To assess the following parameters with gadopiclenol and gadobutrol
  - ✓ lesion visualization (based on 3 co-primary criteria: border delineation, internal morphology and degree of contrast enhancement) assessment by investigator
  - ✓ Subgroup analysis by organ and body region of the 3 lesion visualization co-primary criteria
  - ✓ Improvement in lesion visualization scores at patient level
  - ✓ Technical adequacy of images
  - ✓ Number, size and location of lesions
  - ✓ Diagnostic confidence
  - ✓ Impact of contrast-enhanced MRI on patient treatment plan
  - ✓ Percentage enhancement (E%) of lesion(s)

- ✓ Lesion to Background Ratio (LBR)
- ✓ Overall diagnostic preference
- To assess the safety profile of gadopiclenol and gadobutrol

## 1.2. Trial design

The trial has a prospective, multi-center, randomized, double-blind, controlled and cross-over design.

The Investigational Medicinal Products (IMPs) used during the trial are gadopiclenol and gadobutrol. Patients will perform a screening visit (V1) to confirm trial eligibility, then will be randomized in the trial to determine the order of IMP injection. The randomization scheme will allocate patients in a 1:1 ratio to the two series, gadopiclenol-gadobutrol or gadobutrol-gadopiclenol. Each of the 2 MRI visits (V2 and V4) will be followed by a safety visit (V3 and V5) performed 1 day after the MRI visit.

Images will be evaluated by prospective evaluation of the blinded images in a centralized and blinded manner. The blinded image evaluations (off-site read) will be performed by 3 independent blinded radiologists for the reading of random images and by 3 additional independent blinded radiologists for the global pairs assessment.

As different body regions are included in the study, readers with different expertise were needed for the reading of study images. Hence, according to the different anatomic locations, a pool of 18 readers are selected and qualified for the entire study images reads:

- 6 readers for Head and Neck (H&N): 3 readers for global pairs assessments, 3 readers for all other assessments
- 6 readers Thorax (including breast), Abdomen (including liver, pancreas and kidney), Pelvis (including uterus, ovary and prostate) put together and labelled as Body
- 6 readers Musculoskeletal (including extremities) (MSK)

Within each of the 3 groups, 3 readers are allocated for global pairs assessments, 3 other readers for all other assessments (such as lesion visualisation parameters). Each group of readers will only read images as labelled by specific anatomic locations (H&N, Body and MSK).

As statistical analysis will be performed on the whole set of patients, 1 reader from each expertise domain are put together (1 reader H&N + 1 reader Body + 1 reader MSK), 3 times. So, each reader presented in the report is a combination of 3 readers.

For almost all analyses including the 2 primary analyses, readers are put together based on the numbering (reader 1, reader 2 and reader 3) allocated by the imaging CRO in charge of the reading at the beginning of the trial before the start of the reading.

	Body	MSK	H&N
Reader 1= B1+MSK1+ H&N1	reader B1	reader MSK1	reader H&N1
Reader 2= B2+MSK2+ H&N2	reader B2	reader MSK2	reader H&N2
Reader 3= B3+MSK3+ H&N3	reader B3	reader MSK3	reader H&N3

In addition, Sensitivity analyses of the primary analyses using another affectation of readers from each expertise domain in each reader will be performed. The aim is to have a more homogeneous panel of readers, these sensitivity analyses will be run using grouping together the readers leading to have the 3 readers with the most homogeneous number of patients with matching lesions. Therefore, for the analyses pre vs paired in the gadopiclenol arm on one hand and for the analyses gadopiclenol vs. gadobutrol on paired images on the other hand, readers will be built by selecting the combination of readers from each expertise

domain for which the differences of the sum of each reader compared with the sum of the average across readers is minimal (see table below for an example).

	Body	MSK	H&N	
Reader 1	Radiologist B1	Radiologist MSK1	Radiologist HN1	Sum Reader1
Reader 2	Radiologist B2	Radiologist MSK2	Radiologist NH2	Sum Reader2
Reader 3	Radiologist B3	Radiologist MSK3	Radiologist HN3	Sum Reader3
	Average Body	Average MSK	Average H&N	Sum average

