#### 3.2. Null and alternative hypothesis

For FDA, the primary objective 1 is to be achieved for at least two readers out of three.

For EMA, both primary objectives 1 and 2 are to be achieved for at least two readers out of three.

#### Primary objective 1

The null hypothesis is that the difference in mean scores between Paired images and Pre contrast images for each of the 3 co-primary criteria is equal to 0.

*Mean (SD) of the difference between combined unenhanced and gadobutrol-enhanced imaging vs unenhanced imaging (N = 336).*

Reader	Border delineation	Internal Morphology	Degree of Contrast Enhancement
1	0.67 (0.66)	0.62 (0.47)	1.26 (0.61)
2	0.72 (0.78)	0.82 (0.61)	1.59 (0.77)
3	0.43 (0.50)	0.41 (0.52)	1.06 (0.51)

Considering that in the current trial the scale used is not exactly the same (4-point scale instead of 3-point scale for one parameter) and to account a possible greater heterogeneity, the expected difference is set to 0.35 and the expected standard deviation is set to 1.5.

Hence, expecting that for each of the 3 co-primary criteria, the difference in mean scores will be 0.35 ([“Paired” – “Pre”] within patient) with 1.5 standard deviation, a sample of 200 patients in the gadopiclenol group will have 90% power when using a single group superiority t-test with a 0.025 one-sided significance level.

As a 20% drop-out rate is expected, sample size increases to 250 patients. During the course of the study, the rate of non-valid primary criteria 1 was assessed and was eventually greater than expected (from 20% to 33%) leading to an increase of the sample size from 250 to 300 to maintain statistical power.

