## 5.6. Efficacy evaluation

### 5.6.1. Primary analysis of the primary criteria

#### Superiority of Paired versus Pre contrast images of gadopiclenol regarding lesion visualization co-primary criteria (primary criteria 1)

Each co-primary criterion will be analyzed using a general linear model for each reader independently, modelling the patient's score as a function of the MRI modality ("Pre" MRI and "Paired" MRI) with adjustment on repeated measures on the patient due to the pairing of MRI modalities in patients.

Hence for each off-site reader, the models will be the following:

- Border delineation = MRI modalities + error
- Internal morphology = MRI modalities + error
- Degree of contrast enhancement = MRI modalities + error

The parameters of the general linear model will be estimated using the SAS® procedure Mixed. The procedure used for the superiority analysis will be the following for each co-primary criterion and each off-site reader:

```
proc mixed data = XXX method = REML;
  class subject MRI;
  model eval = MRI;
  repeated MRI / subject=subject / type = cs;
/* To get the one-sided p-value of the paired t-test*/
  lsmeans MRI / pdiff = controlu('PRE') tdiff cl alpha = 0.025;
/* To get the estimate and the corresponding confidence interval of the paired difference */
  lsmeans MRI;
  estimate "PAIRED - PRE" MRI 1 -1 /cl;
run; .
```

For gadopiclenol, the difference "Paired" -"Pre" for each of 3 co-primary criteria will be analyzed using two-sided paired t-tests on the FAS1 on matching lesions. Results will be presented per off-site reader.

In order that superiority of the "Paired" MRI over the "Pre" will be statistically demonstrated, 2 out of 3 readers will have to meet the alternative hypothesis for the three co-primary criteria in the gadopiclenol group: a statistically significant (one-sided p-value is equal or less than 0.025) positive difference in mean scores in border delineation, internal morphology and degree of contrast enhancement of lesions.

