**Body region**

Descriptive statistics:

The 3 co-primary criteria will be summarized by contrast agent groups, MRI modalities (pre and paired) and body regions using FAS1 and FAS2. Analysis using FAS 1 will show only co-primary criteria when gadopiclenol is administered.

Model:

In addition to the primary analyses, sensitivity analyses of the superiority analysis (on the FAS1) and of the non-inferiority analysis (on the FAS2) will be conducted using the same linear model with body region as additional factors.

The model syntax will be as follows for the sensitivity analysis of the superiority:

```
proc mixed data = XXX method = REML;
  class subject MRI body;
  model eval = MRI body MRI*body;
  repeated MRI / subject=subject / type = cs;
  lsmeans MRI body MRI*body / pdiff = controlu('PRE') tdiff cl alpha = 0.025;
  estimate "PAIRED - PRE" MRI*body 1 -1 ..../cl;
run; .
```

The model syntax will be as follows for the sensitivity analysis of the non inferiority:

```
proc mixed data = XXX method = REML;
  class subject GBCA body period;
  model eval = GBCA body period GBCA *body;
  repeated GBCA / subject=subject / type = cs;
  lsmeans GBCA body GBCA*body / pdiff = controlu('gadobutrol') tdiff cl alpha = 0.025;
  estimate "gadopiclenol - "gadobutrol" GBCA*body 1 -1 ..../cl;
run; .
```

The robustness of MRI modality or GBCA effect across different body regions will be discussed with following information:

- Descriptive summary statistics for each body region
- Body region effect and body region \*MRI modality/GBCA interactions tests. These tests are used as exploratory indexes meaning that conclusions of these tests are just used as a support for discussion. Absence of statistical significance should not be taken to imply consistency. Absence of statistical significance in an interaction test, or only directional consistency, would not be sufficiently sensitive filters to detect differences of potential interest.
- Effect estimations for each body region with the associated 95% two-sided CI. Overlapping of all body regions CI estimates with the confidence interval for the overall effect will be checked.
- Graphical visualization of the Body regions with a Forest plot for each body region of the LS Means difference and also the LS Means Ratio.

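### The per-reader body-region interaction test cannot separate H&N, Body and MSK differences from differences between radiologists, so the discussion of consistency across regions can be misread in either direction

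*SAP*

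**What the plan says.** SAP 1.2 sets up three panels by expertise: H&N, Body (thorax, abdomen and pelvis) and MSK. Each panel has three radiologists for lesion visualization, nine in all, and there is no cross-reading: "Each group of readers will only read images as labelled by specific anatomic locations (H&N, Body and MSK". For analysis, one radiologist from each panel is joined to form a reader: "So, each reader presented in the report is a combination of 3 readers". I call this a composite reader.

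SAP 5.6.1 fits the primary models by composite reader: "Each co-primary criterion will be analyzed using a general linear model for each reader independently". The body-region section of SAP 5.6.2 reuses them. The sensitivity analyses "will be conducted using the same linear model with body region as additional factors", coded "model eval = MRI body MRI*body" for objective 1 and "model eval = GBCA body period GBCA *body" for objective 2. Body region has five levels (SAP 2.1). Neither model has a radiologist term.

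The stated use is: "The robustness of MRI modality or GBCA effect across different body regions will be discussed with following information". That information includes the region effect, the interaction test, the region estimates and the overlap of their intervals with the overall interval. The SAP calls the tests exploratory and warns that a non-significant result does not show consistency. It gives no warning about what a significant result may mean.

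**The concern.** Within one composite reader, the panel determines the radiologist. A radiologist who tends to record larger or smaller Paired-Pre gains will look like a region with a larger or smaller gain. Five regions give 4 interaction degrees of freedom. The 2 that contrast H&N, Body and MSK mix region with radiologist. The 2 among thorax, abdomen and pelvis do not, because one radiologist reads all three.

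No other planned analysis separates the two sources. The alternative grouping of readers in SAP 1.2 only re-pairs radiologists across panels. The global model adds reader but has no body term and covers only the agent comparison. The lesion-level models carry reader and center, not radiologist within panel.

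At stake is what the region discussion may conclude. A flagged H&N or MSK difference may be one radiologist's use of the scale, and a real regional difference may be cancelled by it.

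**Working it through.** **The plan's own figure.** The documents state no operating figure for the interaction test, so I checked the sample size that it inherits. Objective 1: n = (1.5 × (1.960 + 1.282) / 0.35)² = 193 by the normal approximation and 195 by the t-test; power at 200 is 90.7%. Objective 2 (margin 0.35, SD 1.75): 197 and 199; power at 200 is 80.4%. Both agree with the stated 200. Inflation gives 200 / 0.67 = 299, against 300 enrolled.

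**Inputs from the documents.** The sample-size table (protocol 11.2, repeated in SAP section 3) gives "Mean (SD) of the difference between combined unenhanced and gadobutrol-enhanced imaging vs unenhanced imaging (N = 336") for three readers of the same patients:

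| | Reader means | Range | Between-reader SD | Average patient SD |
|---|---|---|---|---|
| Border | 0.67, 0.72, 0.43 | 0.29 | 0.155 | (0.66+0.78+0.50)/3 = 0.65 |
| Morphology | 0.62, 0.82, 0.41 | 0.41 | 0.205 | (0.47+0.61+0.52)/3 = 0.53 |
| Enhancement | 1.26, 1.59, 1.06 | 0.53 | 0.268 | (0.61+0.77+0.51)/3 = 0.63 |

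**Assumptions.** There are 200 evaluable patients per composite reader: H&N 25, thorax 50, abdomen 60, pelvis 30, MSK 35. The protocol sets minimums of 25, 50, 25 and 25 for thorax, abdomen, pelvis and MSK, and none for H&N. The true Paired-Pre effect is the same in every region. Radiologists in this trial differ as the table's readers do.

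**Method.** With complete pairs, the MRI*body test equals a one-way F test (4 and 195 df) on the patients' Paired-Pre differences. If region r, with n_r patients, is read by a radiologist whose mean gain is m_r, the noncentrality is λ = Σ n_r (m_r − m̄)² / SD².

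**One worked case (border).** Give H&N (25 patients) the gain 0.67, Body (140) 0.72 and MSK (35) 0.43.
- m̄ = (25×0.67 + 140×0.72 + 35×0.43) / 200 = 0.663.
- Σ n(m − m̄)² = 25×0.007² + 140×0.057² + 35×0.233² = 2.356.
- At SD 0.65, λ = 2.356 / 0.4225 = 5.58, and the nominal 5% test rejects in 43%.
- At SD 1.5, λ = 2.356 / 2.25 = 1.05, and it rejects in 11%.

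Over the six ways of assigning these three gains to the panels, rejection runs from 27% to 55% at SD 0.65 and from 8% to 13% at SD 1.5.

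**Average over random radiologists** (normal effects with the between-reader SDs above; ranges are over repeated runs):

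| | Table SD | SD 1.5 |
|---|---|---|
| Border | 33-36% | 11% |
| Morphology | 60-62% | 15-16% |
| Enhancement | 66% | 23-25% |

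- Restricted to thorax, abdomen and pelvis, the test stays at about 5%.
- With H&N 15 and MSK 25, the rates at the table's SDs fall to about 28%, 52% and 55%.
- With the table's three means fixed and four other region mixes, averages run 19-85% at SD 0.8 and 8-31% at SD 1.5.

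**Agent comparison.** The documents give no reader-level agent differences. With an assumed reader SD of 0.05-0.15 and patient SD √2 × 0.80 = 1.13, GBCA*body rejects in about 6-16%.

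**The case against.** The tests are exploratory, and SAP 5.6.2 says that they support discussion alongside descriptive and clinical assessment. This stands. A reader might infer that the multi-region indication rests on this test, or that the primary error rates are inflated. The documents support neither: success is defined on all regions together, and no success criterion uses the interaction.

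The output already allows a check. Each composite reader's H&N or MSK estimate is a single-radiologist estimate, and three are reported per region. All three composite readers flag in only about 5%, 22% and 28% of trials at the table's SDs (assumed correlation of 0.5 between readers of the same patient). This is real but partial protection: at least two flag in 30-72%, and the SAP sets no rule on agreement for region tests.

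The inputs are borrowed. The reader SDs rest on three readers (2 df; a 95% interval of about 0.52 to 6.3 times the estimate) in a CNS study whose scale the protocol says is not exactly the same. The sponsor raised the patient SD to 1.5 to allow for heterogeneity. This limits the size of the effect, not its existence.

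The reach is partial. A radiologist's constant level shift cancels in the within-patient difference, although the region main effect stays exposed. If the agents do not differ, a radiologist who merely stretches the scale creates no GBCA*body interaction. The five organs named for the organ analysis all belong to the Body panel.

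Dropping H&N and MSK from the tests would depart from protocol 11.4.7. That is a reason to add analyses rather than remove them.

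**Conclusion.** The confounding follows from the SAP's text and needs no assumption: the H&N/Body/MSK part of each per-reader interaction test (2 of 4 df) cannot be separated from radiologist. It would be too strong to call the whole region analysis uninterpretable, since the thorax/abdomen/pelvis part is sound.

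The size does rest on assumptions: the region counts and the reader spread from the cited CNS study. On these, the false-flag rate per composite reader for MRI*body runs from about 11% (border, SD 1.5) to 66% (enhancement, table SD), against a nominal 5%. The evidence for GBCA*body is weaker, because its 6-16% depends on an assumed reader SD. The consequence is a misread discussion of consistency across regions, in either direction. The primary conclusions are untouched.

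**What to change.** Keep the protocol's five-region models, estimates and forest plots. In the body-region section of SAP 5.6.2:

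1. Add the per-reader MRI*body and GBCA*body tests restricted to thorax, abdomen and pelvis, and use these as the test of region consistency. They speak only for those three regions.
2. For H&N versus Body versus MSK, add one model per criterion on the nine radiologists' patient-level differences, with panel fixed and patient and radiologist within panel random. Base panel conclusions on it. For objective 2, include sequence so that the period effect is still carried. The patient term is essential: with no radiologist differences and a correlation of 0.5 between readers, an F test on the nine radiologist means alone rejects in about 35% of trials.
3. State that the per-reader H&N/Body/MSK contrasts are confounded with radiologist, and label those estimates by radiologist. Treat organs outside the Body panel the same way in the organ analysis.

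The cost is SAP wording, one restricted test per reader and one extra model per criterion and objective. No new reads are needed. The limit is precision. With three radiologists per panel, an approximate F test (2 and 6 df) has only about 24-52% power for a true H&N difference of 0.35 at the table's SDs, so the panel comparison can show little beyond large differences.

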## 2. EVALUATION CRITERIA

### 2.1. Demographic, other baseline characteristics and MRI examination

Demographic parameters are age, sex, race, ethnic data, childbearing potential, body weight, height, and body mass index (BMI).

BMI is calculated as follow:  $BMI = \frac{BodyWeight(Kg)}{Height(m)^2}$

Age will be categorized as follow: <65 and  $\geq 65$  years

Country will be categorized in Geographic regions as follow:

- United States of America : North America
- Mexico: Latin America
- Republic of Korea: Asia Pacific
- Hungary, France, Spain, Italy, Poland, Ukraine, Germany, Bulgaria: European countries

Other baseline characteristics are

- Imaging procedure documenting the trial disease
- Trial disease
- Medical history and concomitant diseases
- Patient' intolerance history related to contrast agent
- Prior medications defined as medications ended before the first administration.

Medical history and concomitant diseases will be coded in SOC and PT using the MedDRA latest version available at the date of data base lock. Medical histories are the ones flagged as "Not Ongoing" and concomitant diseases are those flagged as "Ongoing" at the screening visit.

Prior medications are defined as medications ended before the first administration and will be coded using the WHODRUG dictionary latest version available at the date of data base lock.

MRI examination parameters are:

- MRI machine manufacturer name
- MRI machine field strength in tesla (1.5 or 3.0)
- Imaged body regions: Head and Neck, Thorax, Abdomen, Pelvis and Musculoskeletal

CONFIDENTIAL	STATISTICAL ANALYSIS PLAN PHASE III TRIAL GDX-44-011 VERSION NO. 2.0      DATED 25 JANUARY 2021	████████ Page 9 / 57
--------------	---	-------------------------

